1 ABBREVIATIONS

| | |
|--------|--|
| AE | Adverse event |
| ADE | Adverse device effects |
| CRF | Case report form |
| CRO | Contract research organisation |
| DD | Device deficiency |
| eCRF | Electronic case report form |
| ED-SSU | Emergency Department - Short Stay Unit |
| GCP | Good clinical practice |
| HREC | Human Research Ethics Committee |
| IFU | Instruction For Use |
| JSI | JiffyStent Inserter |
| KUB | Kidney, ureter and bladder |
| LTFU | Lost to follow-up |
| NHMRC | National Health and Medical Research Council |
| PI | Principal Investigator |
| QMS | Quality management system |
| SAE | Serious adverse event |
| SSI | Significant Safety Issue |
| TGA | Therapeutic Goods Administration |
| USADE | Unanticipated Serious Adverse Device Effect |
| USM | Urgent Safety Measure |

2 REVISION HISTORY

| Version Number | Version Date | Revisions |
|----------------|--------------|------------------------|
| 1.0 | 22 Jan 2024 | N/A – initial document |

3 SYNOPSIS

| Clinical investigation plan | |
|-------------------------------|---|
| Title | A feasibility pilot study of the efficacy, reliability, safety and patient experience of the JiffyStent ureteric stent inserter. |
| Short title | Evaluation of the JiffyStent Inserter in patients requiring a ureteric stent. |
| Protocol No. | JSI001 |
| Investigational device | |
| Name | JiffyStent Inserter |
| Description | The JiffyStent Inserter is a single-use device which allows visualization of the ureteric orifice and subsequent insertion of a ureteric stent, which is pre-loaded by the health professional, into the ureter. |
| Indication for use | The JiffyStent Inserter enables temporary stenting of the ureter in adult patients with ureteral or renal obstruction due to an acute ureteric stone or ureteric stricture. |
| Clinical investigation design | |
| Background | 
The incidence of renal colic, or pain caused by a blockage in the urinary tract, varies depending on the population studied. In general, it is estimated to affect around 10-15% of the population at some point in their lives.
 
The intention is to perform a proof-of-concept pilot study where the JiffyStent Inserter (JSI) will be used to insert a stent into participants who require a stent or have kidney blockage and pain from a stone in the ureter.
 
A positive outcome of the proposed study will lead to a pivotal clinical trial suitable for regulatory approval for the JSI.
 
The main objectives of the proposed trial are to evaluate the safety, feasibility and clinical efficacy of the JiffyStent Inserter. The study will:
 
 • Ensure that the JSI device works reliably. • Ensure JSI successfully inserts a ureteric stent in the ureter of participants. • Obtain preliminary evidence of safety. • Evaluate participant recruitment rate. • Assess participant experience and satisfaction with the JSI. |

| | |
|--|--|
| Aim | This study aims to evaluate the reliability, safety, clinical efficacy, and participant satisfaction using the JiffyStent Inserter. |
| Design | Single centre, first-in-human feasibility and safety pilot trial. |
| Hypothesis | The JiffyStent ureteric stent inserter can reliably, safely, quickly, effectively and to the participant's and doctor's satisfaction, insert a ureteric stent into the ureter of a participant with renal colic. |
| Methods | Eligible participants will be enrolled and have a ureteric stent inserted by the JiffyStent Inserter. |
| Endpoints | 
Primary endpoint
 
The ability of the JiffyStent Inserter to correctly insert a stent into the ureter of a suitable participant as determined by a post-stenting kidney, ureter, and bladder (KUB) plain X-ray.
 
Secondary endpoints
 
 • The mechanical reliability of the JSI to perform its function as expected. • The clinical safety of the JSI • Time taken to insert the ureteric stent using JSI. • Feasibility- evaluation of participant recruitment rate • Participant experience and satisfaction with the JSI User satisfaction for urological doctor/study researcher • Impact on workflow data • Impact on health economics |
| Trial Registration | ACTRN12623000264684p |
| Arms and interventions | Single arm: participants receiving treatment with JiffyStent Inserter. |
| Follow-up visits | Follow up visit for definitive stone treatment operation (usually within 14-21 days). |
| Study duration | Study duration for participant: 14-21 days. Encompasses screening, consent, intervention and ceasing at definitive stone treatment operation visit. Total study duration: six (6) months |
| Clinical investigation population | |
| Sample size | Up to 15 participants ≥ 18 years old |
| Key Inclusion criteria | 
 • Consenting adult patient male or female, age ≥ 18 years old. • Patient about to undergo stent insertion as part of their routine urological care. |

| | |
|-------------------------------|--|
| | 
 • Ability to provide informed consent signed by study participant. • Willingness and ability to comply with study-related procedures/assessments |
| Key Exclusion criteria | 
 • Age <18 years • Known allergy to local anaesthetic lubricating gel, Pentrox “green whistle” inhaler anaesthetic • Stone larger than 1cm • Stone impacted in ureter. • Men with prostate larger than 100cc in size • Patient with severe sepsis requiring nephrostomy or stabilisation in an operating room |
| Statistical analysis | |
| Analysis sets | N/A |
| Statistical design | This is an initial feasibility study. Outcomes will be summarized using descriptive statistics. There is no pre-specified power calculation |

4.3 Roles And Responsibility

This clinical investigation is sponsored by JiffyStent Pty Ltd (sponsor), located in Heidelberg, Victoria. An agreement between the involved site and the Sponsor will be set in place before the start of the study. This agreement details the specific roles and obligations of the site and the Sponsor, processing of data, confidentiality, insurance policy, publication policy, termination policy, applicable laws, and financial provisions.

The Sponsor is responsible for selecting qualified investigators and will provide information to the investigators to conduct the clinical investigation properly, which includes training on the device. The sponsor will further ensure proper monitoring and ensures the study is being conducted in accordance with this CIP. The Sponsor may delegate responsibilities, such as study management and monitoring, to a contract research organization (CRO).

The principal investigator (PI) will be a legally qualified clinician, trained in urology. Their qualification and experience will be assessed during a site feasibility visit. As study investigator, they are further responsible to protect the rights, safety, and welfare of subjects in the clinical investigation, ensure that informed consent is properly obtained and to ensure that the investigation is conducted appropriately. As principal investigator, they will act as team leader and will make sure that the involved team of co-investigators and study coordinators are appropriately trained on the protocol and procedures.

5 BACKGROUND

5.1 Lay Summary

A common presentation to the emergency department is a patient in excruciating pain from a kidney stone obstructing the ureter and kidney. Many of these patients will require a ureteric stent to relieve the obstruction and their pain. The current best treatment is to admit these patients to the operating room and insert a ureteric stent with the patient under general anaesthetic. This process can take 24 hours or more. The JiffyStent Inserter (JSI) is an innovative single use medical device that allows the Urologist or Emergency Department Physician to insert a ureteric stent while the patient is in the emergency room. This is a proof-of-concept study to show that the JSI works as desired by correctly inserting a stent into the ureters of participants, initially under controlled conditions in the operating room, and then in the emergency department. It is anticipated that use of the device will take 3-5 mins. If a stent cannot be inserted with the JSI after the first attempt, then a stent will be inserted in the operating room by the standard procedure. The outcome of every JSI and the success of the stent insertion will be recorded by the trial team by medical record review and discussion with the treating doctor. The study will involve up to 15 participants under controlled conditions. Of the 15 total participants, five (5) will be individuals who require a stent as a standard part of their urological procedure and 5-10 participants will be individuals who present to the emergency room with acute renal colic from a kidney stone and require a ureteric stent insertion. A successful outcome will lead to a pivotal multicentre clinical trial necessary for regulatory approval thereby making the JiffyStent Inserter available for widespread use.

5.2 The burden of ureteric stones and acute renal colic

Acute renal colic is the sudden onset of severe flank pain originating over the costovertebral angle and radiating to the groin or testicles. It is associated with nausea, vomiting, and in some cases, visible haematuria.

5.2.1 Incidence

Acute renal colic is mainly caused by the obstruction of the urinary tract by the presence of a stone. Nephrolithiasis or kidney stones is a common condition with prevalence rates of 5% - 15% in the population. Yearly incidence of acute renal in North America and Europe is in the range of 0.2% to 0.5%. It is most likely (>70%) to occur in patients between the ages of 20 and 50. More likely in men than women by a factor of 2:1[1-4]. Risk factors include obesity, hypertension, family history, IBS, and diabetes.

5.2.2 Causes

Pain is often caused by a combination of ureteral muscle spasms, increased proximal peristalsis, localized inflammatory changes, renal swelling with capsular stretching, edema, and irritation. These, in turn, stimulate submucosal stretch

receptors in the ureter, renal pelvis, and capsule. Stimulation of the renal pelvis, peri pelvic renal capsule, and calices from stretching most closely mimic renal colic.

Patients often report dull constant pain with colicky episodes. While constant pain is linked to stretching of the renal capsule due to obstruction, colicky pain can be attributed to peristalsis of the ureteral smooth muscle.

5.2.3 *Factors Associated with Surgical Intervention*

Factors associated with earlier surgical intervention are - severe hydronephrosis; ureteral stone $\geq 9\text{mm}$; >700 Hounsfield units stone density; ≥ 0.2 cc stone volume; $>2\text{mm}$ ureteral wall thickness; extrarenal pelvis; anterior-posterior diameter of renal pelvis $>18\text{mm}$. [5, 6]

Up to 95% of stones $>8\text{mm}$ require intervention to pass. Patients with infected stones need operative intervention to prevent severe and life-threatening sepsis.

5.2.4 *Current Standard of Care*

The current standard treatment for participants presenting to the emergency department-short stay unit with acute renal colic due to an obstructing ureteric stone is to give them pain relief, admit them to hospital, and then find a time in the operating room to insert a stent. This operating slot may be on a regular list or on the emergency operating list. Patients will often wait over 24 hours to have their stent inserted in the operating room with all the burden of prolonged fasting, recurrent pain, prolonged obstruction of the kidney with risk of kidney impairment, infection, and time away from home.

6 INVESTIGATIONAL DEVICE

6.1 **Manufacturer**

JiffyStent Pty Ltd (Victoria, Australia) is the legal manufacturer of the JiffyStent Inserter.

6.2 **JiffyStent Inserter**

The all-in-one single use JiffyStent Inserter allows visualization of the ureteric orifice and subsequent insertion of a pre-loaded ureteric stent into the ureter for the purpose of alleviating ureteric or renal obstruction due to an acute ureteric stone. The value of the JSI is that it will rapidly alleviate the participants pain without the need to go to the operating room. This will significantly reduce the time the participants experience pain; reduce burden on emergency department waiting times for hospital beds; reduce opportunity costs for emergency operating lists; reduce the inconvenience to surgeons waiting prolonged periods for emergency operating slots (often very late at night); markedly reduce the cost of treating ureteric stones for the health system. The system will be in contact with the body

(i.e., urinary tract system).

Additional information about the identification and description of the investigational device may be found in the current version of the Investigator Brochure EDIB-20100106-01_00. The JSI does not contain medicinal substances, human, or animal tissues or their derivatives of other biologically active substances.

6.3 Regulatory Classification

The JiffyStent Inserter is considered a class IIA device according to the *Therapeutic Goods (Medical Devices) Regulations 2002* (Australia), based on the following rule:

- Rule 3.2 (1): Surgically invasive medical devices intended for transient use.
 - (1) This clause applies to a surgically invasive medical device that is intended for transient use.
- (2) Subject to subclauses (3) to (5), the device is classified as **Class Ila**.

6.4 Identification of Investigational Device

JiffyStent Inserter device number JSI-03_03 will be used for the purposes of this study.

6.5 Intended purpose in the clinical investigation

In this clinical investigation, the intended purpose of the JiffyStent Inserter is to allow visualisation of the ureteric orifice in participants who are about to undergo stent insertion as part of their routine urological care.

6.6 Intended populations and indications

The intended populations are adults ≥ 18 years who are about to undergo stent insertion as part of their routine urological care or have presented to the Emergency Department - Short Stay Unit (ED-SSU) with acute renal colic requiring admission to hospital for a ureteric stent.

6.7 Required training and experience

Investigators will be trained to use the investigational device (JiffyStent Inserter). The investigators working with the JSI will be legally qualified clinicians (e.g., urologists) trained in performing endoscopic ureteric procedures. The investigators will be trained prior to the use of the investigational device (JiffyStent Inserter) by the Sponsor, JiffyStent, on the Instructions for Use (IFU) and the study protocol. Training will also include a demonstration of the device. All investigators will receive the same amount of virtual and in-person training.

Additionally, investigators shall have adequate qualifications with regards to the project specificities, including:

- Experience and training in clinical studies, particularly clinical studies involving medical devices, and Good Clinical Practices for Medical Devices (ISO 14155:2020);
- Able to read and understand English.
- On-site initiation visits will be organised, in which full training will be given to all appropriate staff members participating in the clinical investigation, including principal investigators, study coordinators, and any other site personnel pivotal to the conduct of the clinical investigation. This training will include at least the following: instructions on the functions and use of the investigational device, procedure outlines in the clinical investigation plan, main principles of Good Clinical Practices for Medical Devices (ISO 14144:2020), instructions on completion of case report forms, content of the investigator site file, and management of device deficiencies.

6.8 Device traceability

Access to investigational devices will be controlled and the investigational devices will be used only in the clinical investigation and according to the clinical investigation plan. The sponsor will keep records to document the physical location of all investigational devices from shipment of investigational devices to the investigation sites until return or disposal. The sponsor shall have instructions in place and make packaging materials available, if applicable, for the safe return or disposal of investigational devices, including potentially hazardous devices. The devices will be identified by a serial number and expiry date. One device will be used per participant.

6.9 Investigational device and comparator

One (1) JiffyStent Inserter device will be used per participant. There will be no comparator device.

6.10 Medical/Surgical procedures

Participant is positioned in supine position following adequate analgesia, sterile prep and drape is applied to the perineum. JiffyStent Inserter settings are adjusted to individual participant measurements (pre-determined by abdominal imaging) and ureteric stent loaded into investigational device. JiffyStent Inserter is powered on and connected to smart device. The JiffyStent Inserter proboscis is inserted into the urethra and advanced to the bladder. The ureteric orifice is visualised via the smart device and the wire with ureteric stent is inserted into the ureteric orifice. The spool is rotated thereby advancing the wire and stent up the ureter. This rotation is continued until its limit and then the JSI guidewire spool is rewound to its limit and the stent is seen curling in the bladder. The JSI is removed from the urethra and participant leaving the ureteric stent insitu. A kidney, ureter and bladder (KUB) x-ray is performed to confirm stent positioning.

7 JUSTIFICATION FOR CLINICAL INVESTIGATION DESIGN

7.1 Pre-clinical testing

In conducting our pre-clinical testing procedure, we were able to successfully demonstrate the key functions in dummy models. We successfully loaded the stent into the JSI and inserted the battery, switching the camera on without a hitch. The device was synced up to Wi-Fi, displaying clear vision from the camera on the connected app. Saline fluid was flawlessly affixed and running optimally.

Our researchers then proceeded to insert the apparatus into the bladder via the urethra. The ureter opening was swiftly located and clearly visible throughout the process. Utilizing cutting-edge technology, we were able to visualize both the guide wire and the stent entering the ureter opening accurately. Subsequently, the stent was advanced fully, and the guide wire was retracted entirely without any challenges.

During the entire procedure, the camera remained reliably connected while the stent placement within the bladder was clearly visualized. The JSI was subsequently removed without any complications. Post-procedure, an (visual/imaging by opening/removing the lid of the model) validated the correct positioning of the stent. The JSI was disposed of following all standard guidelines.

The duration to complete the sequence of this particular experiment averaged between 3-6 minutes. This streamlined process, allied with meticulous attention to procedure, ensured the successful completion of every task. For further information see document “Investigator Brochure EDIB-20100106-01_00.docx”

Physical Simulation Model

A specialized ureteral anatomy model has been used to test the JSI. This model offers a comprehensive representation of the entire urinary tract from the external urethral meatus at the tip of the penis to the ureter connecting to the bladder and its vital connection with the kidney.

Non-clinical pharmacology

No non-clinical pharmacology has been undertaken.

7.2 Clinical development stage

This clinical investigation is a first-in-human, feasibility study. It is used to capture preliminary safety and performance information on the final design of the JiffyStent Inserter.

7.3 Evaluation of clinical data

As this clinical investigation is a first-in-human, feasibility study there is no clinical data for evaluation.

8 OBJECTIVES

8.1 Aim

This study aims to evaluate the reliability, safety, clinical efficacy, and participant satisfaction using the JSI.

8.2 Hypothesis

That the JiffyStent Inserter can reliably, safely, quickly, effectively and to the participant's and doctor's satisfaction, insert a ureteric stent into the ureter of a participant with renal colic.

8.3 STUDY OUTCOME MEASURES

8.3.1 Primary endpoint:

- The ability of the JSI to correctly insert a stent into the ureter of a suitable participant as determined by post-stenting KUB plain X-ray.
 - Timepoint: Immediately post-stent insertion with KUB Xray
 - Measure: Investigator's assessment of position of superior part of stent within kidney collecting system on KUB plain X-ray performed after stent insertion (Yes/No/Unsure)
 - If "Unsure"- proceed to renal ultrasound to confirm.
 - If "No" or still "Unsure" then proceed to standard stent insertion in operating room

8.3.2 Secondary endpoints:

- The mechanical reliability of the JSI to perform its function correctly as determined by the treating doctor as noted on a global doctor satisfaction score.
 - Timepoint: Immediately post-device usage
 - Measure: Rating of device reliability, i.e. correct mechanical function to work as intended on global doctor satisfaction score.
- The clinical safety of the JSI.
 - Timepoint: Immediately post-intervention commencement through to final follow up visit.
 - Measure: Assessed using reported adverse events, device deficiencies and participant questionnaire.
- Time taken to insert the ureteric stent using JSI (measures stent insertion procedure time only, workflow data assesses overall workflow and will be assessed separately).
 - Timepoint: Immediately post-intervention commencement.
 - Measure: Use of stopwatch or calculated from start and end times and recorded on a

case report form.

- Feasibility- evaluation of participant recruitment rate.
 - Timepoint- At study completion. To be completed within 6 months of study commencement.
 - Measure: A log will be kept of all participants invited to the study and if applicable, their reasons for refusal noted. Feasibility will be assessed using recruitment/withdrawal data and an audit of study enrolment and withdrawal logs.
- Participant experience and satisfaction with the JSI.
 - Timepoint: Prior to stent insertion (within 2 hours), Post stent insertion (within 1 hour), and at follow up visit for definitive stone management surgery (within 14-21 days)
 - Measure: Participants will receive a Patient Satisfaction Questionnaire regarding their experience of ureteric stent insertion with the JiffyStent Inserter.
- User satisfaction for urological doctor/study researcher.
 - Timepoint- Immediately after stent-insertion.
 - Measure: Investigators will receive a User Questionnaire regarding their experience of using the JSI. Collated data will be analysed 3-6 months post-intervention commencement.
- Impact on workflow data
 - Measure: Analysis of improvements in workflow including time in the ED-SSU, total length of stay, time utilisation by urology doctors.
 - Timepoint: At follow up visit for definitive stone management surgery (within 14-21 days)
- Impact on health economics
 - Measure: Comparison of costings related to length of stay, admission, operating room utilisation, staffing, equipment.
 - Timepoint: At study completion. A health economist will be engaged to help perform the analysis.

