11.2.2 Device Mechanical Risks

| Hazard | Risk | Mitigation and residual risk |
|---|---|---|
| Device failure or Spools get jammed and fail to work correctly- no stent inserted Probability: Possible Severity: negligible | Stent is unable to be inserted. Minimal harm to participant. | Quality design and manufacture processes and strict adherence to best practice QMS. Procedure abandoned and take to theatre as per standard procedure for stent insertion. |
| Spools get jammed and fail to work correctly- partial stent insertion Probability: Possible Severity: minor | Procedure not completed successfully. Stent half hanging out and may be across urinary sphincter leading to temporary incontinence. | Quality design and manufacture processes and strict adherence to best practice QMS. Procedure abandoned and take to theatre as per standard procedure for removal of stent and insertion of new stent. |

| | | |
|---|---|--|
| 
Incorrect guidewire length set-too long
 
Probability: Possible Severity: serious
 | 
Guidewire inserts too far. Usually, guidewire has floppy end that will curl up in collecting system of kidney. Stent still inserted correctly. Very rarely, guidewire will pierce top of kidney collecting system and stent may be inserted outside of kidney.
 | 
Device has a failproof stop so that the guidewire cannot be inserted more than 33cm. We will use a guidewire with a 3cm floppy tip that will curl if it hits end of collecting system. Device has variable length settings for shorter ureters. These will be related to the height of participant and clearly marked on the device. instructional online video will provide education around ureteric length determination. In the case of no length being set, the guard wire will be limited at 33 centimetres which will be safe in nearly all instances. Post procedure KUB X-ray will confirm correct position of upper end of stent within the kidney collecting system.
 |

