14.3 Analysis of the primary endpoint

Correct placement of the stent into the ureter as visualised on KUB plain x-ray post procedure.

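### The primary endpoint measure has no criterion for the bladder end of the stent, so a partial deployment that the protocol regards as unsuccessful could be scored as a success

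*Protocol*

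**What the plan says.** Section 8.3.1 gives the primary endpoint as "The ability of the JSI to correctly insert a stent into the ureter of a suitable participant as determined by post-stenting KUB plain X-ray". The measure beneath it is the investigator's "assessment of position of superior part of stent within kidney collecting system on KUB plain X-ray performed after stent insertion", answered Yes, No or Unsure. An Unsure film goes on to renal ultrasound. A No, or an Unsure that persists, goes on to standard insertion in the operating room.

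Section 14.3 restates the endpoint for analysis as "Correct placement of the stent into the ureter as visualised on KUB plain x-ray post procedure" and names neither end of the stent. Section 14.5 analyses everyone treated with the device.

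The lower end appears elsewhere. Section 6.10 describes the close of deployment: "the JSI guidewire spool is rewound to its limit and the stent is seen curling in the bladder". The device is then removed and the film taken. Section 11.2.2 lists a spool jam with partial insertion, rated Possible. The described state is "Stent half hanging out and may be across urinary sphincter leading to temporary incontinence", the protocol's verdict is "Procedure not completed successfully", and the participant goes to theatre to have that stent removed and another inserted.

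**The concern.** The device has to do two things: carry the upper end to the kidney, and release the stent so that its lower end lies in the bladder. The protocol's own description of the procedure includes both, but the primary measure tests only the first.

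Section 6.10 has the stent advanced to the spool's limit before the wire is rewound. A fault at the rewind or release step could therefore occur with the upper end already in the collecting system. Read literally, the measure would score that participant Yes, while the risk table regards the procedure as unsuccessful.

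Any such error runs one way, towards a higher success proportion. The synopsis says that a positive outcome will lead to a pivotal trial, and section 15.8 has the safety committee review efficacy after the first five participants. With so few participants, one misclassified case is visible in the headline result.

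**Working it through.** **Passages side by side**

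| Place in protocol | Upper end | Lower end |
|---|---|---|
| 8.3.1, endpoint statement | Not specified (correct insertion into the ureter) | Not specified |
| 8.3.1, measure | In the collecting system: Yes/No/Unsure | Not scored |
| 14.3 | Not specified (correct placement into the ureter) | Not specified |
| 6.10 | Stent advanced to the spool's limit | Seen curling in the bladder |
| 11.2.2, jam with partial insertion | Not stated | Half hanging out, possibly across the sphincter; judged unsuccessful |

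For a partial insertion the measure gives one of three results:

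1. The upper end stopped short of the collecting system. The score is No, which agrees with 11.2.2.
2. The upper end is in the collecting system. The score is Yes, which disagrees with 11.2.2.
3. The procedure is abandoned and no film is taken. The measure, which is read from a film after insertion, gives no score, although the participant is in the 14.5 population and 14.8 rules out imputation.

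The concern is case 2. Case 3 shows that the scoring rule also needs to name abandoned deployments.

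**Size**

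The protocol gives no success threshold, power or derived sample size for this endpoint, so there is no figure of its own to reproduce. The inputs are:

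- up to 15 participants, five in Group 1 and 5 to 10 in Group 2 (9.1), so 10 to 15 in all;
- Possible = 1% (Appendix A, risk score matrix);
- an expected failure rate of 5 to 10% (10.4);
- exact two-sided 97% intervals for categorical variables (14.1).

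*Shift from one case*, 1/n: 1/15 = 6.7 points; 1/10 = 10 points; 1/5 = 20 points at the five-participant committee review.

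*Chance of at least one partial insertion from a spool jam*, 1 − (1 − 0.01)^n:

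- n = 15: 1 − 0.99^15 = 14.0%
- n = 10: 1 − 0.99^10 = 9.6%
- n = 5: 1 − 0.99^5 = 4.9%

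These are ceilings on misclassification from this hazard, since only case 2 is misclassified. The share of jams that fall in case 2 is not given and could be anywhere from none to all. The expected number of such jams in 15 is 15 × 0.01 = 0.15. The 1% is a risk-matrix score, not an observed rate, and it belongs to the jam row. Several rows of 11.2.3 also mention a partly deployed stent, but they give no separate rate for that outcome.

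*Against the expected failures*: 15 × 0.05 = 0.75 and 15 × 0.10 = 1.5. One case scored Yes instead of No could hide most or all of the failures that the protocol expects.

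*Illustration*, assuming every other participant succeeds (Clopper-Pearson 97% limits; with x = n the lower limit is 0.015^(1/n)):

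| n | Case scored Yes | Case scored No |
|---|---|---|
| 15 | 15/15 = 100% (75.6 to 100) | 14/15 = 93.3% (65.3 to 99.9) |
| 10 | 10/10 = 100% (65.7 to 100) | 9/10 = 90% (52.1 to 99.8) |
| 5 | 5/5 = 100% (43.2 to 100) | 4/5 = 80% (24.7 to 99.7) |

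**The case against.** There is a sensible reason to image the upper end. It cannot be seen during the procedure, whereas the bladder end is in the camera's view. The endpoint statement and 14.3 both speak of correct insertion or placement, which leaves an investigator room to fail a stent hanging in the urethra. Bladder-end faults are also recorded elsewhere: as device deficiencies, in the mechanical reliability rating, and in the ease ratings for the spool and for stent disconnection (13.5.3). The study is a descriptive pilot with no success threshold, and at 1% the event is unlikely to occur at all.

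Much of this stands, and it limits the point to a scoring gap of modest expected size. It does not close the gap. The measure does not tell the investigator to use the camera view, and the secondary outcomes do not correct the primary proportion.

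A reader might infer three stronger things that the protocol does not support.

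- *That it treats a stent drawn up out of the bladder as a failure.* No passage describes this. The row on a guidewire set too long regards the stent as usually still correctly placed, and its rare bad outcome is at the kidney end.
- *That every half-hanging stent counts as a success.* It would score Yes only if its upper end were in the collecting system, and 11.2.2 does not say where that end lies.
- *That the two sections give incompatible routes to theatre.* Section 8.3.1 does not say that No or persistent Unsure is the only route, and 11.2.2 deals with an event during the procedure, before the film. Both can be followed. The inconsistency is in what counts as success.

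**Conclusion.** The concern holds as a gap in the scoring rule. The measure in 8.3.1 omits the lower end, which 6.10 makes part of a finished insertion, so it could score Yes for a partial deployment that 11.2.2 regards as unsuccessful. The definitional gap is plain from the text; its frequency is not known.

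Any resulting bias is upward: 6.7 points per case at n = 15 and 10 points at n = 10. Taking the matrix figure of 1% at face value and participants as independent, the chance that a jam produces any partial insertion in 15 is about 14%, and the chance of a misclassified one is no higher than that. That an upper end can be in place while the lower end is undeployed is an inference from the order of steps in 6.10; the protocol does not state it. The matter is worth correcting because the remedy is cheap, not because a distorted result is likely.

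**What to change.** Reconcile 6.10, 8.3.1, 11.2.2 and 14.3 into a single definition of correct placement for scoring:

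- In 8.3.1, score Yes only when the upper end is in the collecting system and the lower end is in the bladder, using the KUB film already planned and the device camera view already described in 6.10.
- In 14.3, use the same definition and score as No any treated participant whose deployment was abandoned or incomplete in the sense of 11.2.2, whether or not a film was taken.

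This alters how the result is scored, not how any participant is managed. The cost is protocol wording and one extra field on the case report form, with no new imaging or visit. The reported success rate may come out slightly lower.
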